6.2. Institutional responsibilities

SAEs will be reported immediately to the PI or MLW Coordinator. All other adverse events will be logged and reported through regular follow-up reports.

As this is a public-health scale-up evaluation, following an intervention trial that showed low risk of harm from HIVST (no suicides from 27,000 HIVST episodes), expected SAEs will be reported through 6-monthly progress reports that will report on safety as well as other important process indicators and will be sent to the Technical Advisory Group members and local and international collaborators.

12 monthly reports with full listings of SAEs will be submitted to Ethics Review Boards at the time of annual reporting.

6.3. Reporting procedures

SAE forms will be completed by the MLW Trial Coordinator and responsible CBDA Supervisor and reported to the PI. The PI will check the form, make changes as necessary.

SAEs will be evaluated for seriousness, and likely relatedness by the PI.

7. Statistical considerations and sample size

7.2. CRT sample size calculations

This trial has one primary and one secondary outcome, with a number of other analyses to be specified in the Statistical Analysis Plan. The sample size considerations here relate to the main Primary Outcome (comparison between arms of recent HIV testing).

A survey sample of 250 to 500 adults per cluster will provide sufficient power for a two sample comparison of unmatched proportions for HTC coverage was performed across the intervention and control arms to determine the number of clusters per arm.

The cluster size is based on the typical size of a rural village (250-500 people) from previous experience in Malawi. Using 2010 DHS data, baseline rates for individuals tested in the last 12 months is estimated at 25% to 40%, with a 45% to 60% predicted effect size in the intervention arm compared to the control arm. Baseline coverage for individuals who have ever tested is estimated at 42% to 60% with predicted effect size 30%-45%.

Figures 10 and 11 contain a table of scenarios for each of the outlined assumptions. To detect a 50% increase in rate of people testing in the past 12 months and a 45% increase in the percentage of people who have ever tested in the intervention villages, there should be approximately 8 clusters per arm and approximately 4,000 participants total. This study will aim to reach 10 clusters per arm and 5,000 participants to provide contingency for a lower than anticipated effect size.

1-type l	Power	Baseline testing	Effect size	Interven- tion testing	Cluster size	k	Number of clusters	Total partici- pants
0.95	0.8	0.35	0.6	0.56	250	0.25	6.19	3094.21
0.95	0.8	0.3	0.6	0.48	250	0.25	6.30	3148.20
0.95	0.8	0.25	0.6	0.4	250	0.25	6.45	3223.78
0.95	0.8	0.35	0.55	0.5425	250	0.25	6.92	3460.38
0.95	0.8	0.3	0.55	0.465	250	0.25	7.05	3523.39
0.95	0.8	0.25	0.55	0.3875	250	0.25	7.22	3611.61
0.95	0.8	0.35	0.5	0.525	250	0.25	7.87	3933.04
0.95	0.8	0.3	0.5	0.45	250	0.25	8.02	4007.80
0.95	0.8	0.25	0.5	0.375	250	0.25	8.22	4112.45
0.95	0.8	0.35	0.45	0.5075	250	0.25	9.12	4560.03
0.95	0.8	0.3	0.45	0.435	250	0.25	9.30	4650.47
0.95	0.8	0.25	0.45	0.3625	250	0.25	9.55	4777.08

Figure 10. Sample size calculation – tested for HIV in last 12 months

Figure 11. Sample size calculation – ever tested for HIV

1-type l	Power	Baseline testing	Effect size	Interven- tion testing	Cluster size	k	Number of clusters	Total partici- pants
0.95	0.8	0.6	0.45	0.87	250	0.25	8.67	4333.93
0.95	0.8	0.5	0.45	0.725	250	0.25	8.79	4397.24
0.95	0.8	0.42	0.45	0.609	250	0.25	8.94	4469.59
0.95	0.8	0.6	0.4	0.84	250	0.25	10.28	5139.67
0.95	0.8	0.5	0.4	0.7	250	0.25	10.44	5218.16
0.95	0.8	0.42	0.4	0.588	250	0.25	10.62	5307.86
0.95	0.8	0.6	0.35	0.81	250	0.25	12.58	6291.61
0.95	0.8	0.5	0.35	0.675	250	0.25	12.78	6391.99
0.95	0.8	0.42	0.35	0.567	250	0.25	13.01	6506.71
0.95	0.8	0.6	0.3	0.78	250	0.25	16.06	8030.49
0.95	0.8	0.5	0.3	0.65	250	0.25	16.33	8164.21
0.95	0.8	0.42	0.3	0.546	250	0.25	16.63	8317.04

Extended individual questionnaire and post-intervention household survey

The sample size for the extended individual questionnaire is based on the minimum sample size needed for the DCE to measure choice probabilities with a high level of accuracy. Though sample size calculations for DCEs have not been formalised in the same manner as trials, conventional sample sizes tend to be around 200 participants per population strata, though new efficient experimental designs do allow for smaller samples.

The study will use five strata in total, generating a sample size of 1,000 participants. Strata of interest include low and high HIV risk, young (16 to 30 years) and old (31 years or more), male and female, self-identified HIV positive and negative, and Socio-Economic Status (SES) quintiles.

8. Results presentation and dissemination

Descriptive and inferential findings will be presented through tables and histograms, line graphs and other figures, where relevant.

The results of this research will be used to guide the introduction of self-testing into community-based HTC models and the formation of national and international policies around HIVST. Results will be disseminated to the MoH HIV Unit, COMREC and UNITAID. A report on the study will be produced and disseminated to COMREC, the College of Medicine (COM) Library, the Health Sciences Research Committee and the University Research and Publication Committee. Findings will also be distributed internationally to global health policy makers, nationally to the Malawian government, and regionally to District and Council Health Offices. Presentations will be given at the COMREC research dissemination day and at MLW research-in-progress meetings. Copies of peer-reviewed publications from the research will be submitted to COM, MLW, and LSHTM.

In terms of public engagement, the MLW-LSHTM team will work with the MLW Science Communication team to disseminate the project results and raise the profile of HIVST in Malawi. MLW actively engages with both urban and rural communities, and has already hosted a range of programmes including science cafes, radio projects, and mobile exhibitions about HIVST. These mediums will be employed to educate the general public about the UNITAID project and the results.

9. Ethical considerations

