1.5 Research findings and dissemination

Early evidence in Malawi points to substantial willingness to self-test and the potential of HIVST products to provide affordable community-based HTC and improve linkages to HIV services. The results of this research will be used to guide the introduction of self-testing into community-based HTC models and the formation of national and international policies around HIVST. Results will be disseminated to the Ministry of Health (MoH) HIV Unit, College of Medicine Research and Ethics Committee (COMREC) and UNITAID. Findings will also be distributed internationally to global health policy makers, nationally to the Malawian government, and regionally to District and Council Health Offices.

2. Background

Malawi has a high HIV prevalence, with an estimated 10.2% of adults living with HIV. Of those who are HIV positive, 46% are on Antiretroviral Therapy (ART) (UNAIDS 2014). In key populations, HIV prevalence is substantially higher than in the general population, with estimated prevalence of 21.4% among Men who have Sex with Men (MSM) and 70.7% among Female Sex Workers (FSWs) (Wirtz, et al. 2014) (Baral, et al. 2009).

Major factors driving new HIV infections in Malawi include lack of knowledge on partner HIV status in serodiscordant relationships, high rates of transactional sex, and low uptake of HIV prevention services including consistent condom use and Voluntary Medical Male Circumcision (VMMC) (UNAIDS 2014). According to the 2010 Demographic and Health Survey (DHS), 9.7% of male respondents had paid for sex at least once, with low condom use (60.7%) during transactional sex (National Statistical Office and ICF Macro 2011). Uptake of VMMC in Malawi was estimated as 2% in December 2012 (UNAIDS 2014).

Reaching the Joint United Nations Programme on AIDS (UNAIDS) 90-90-90 targets (90% of all HIV-positive individuals aware of their status, of whom 90% are retained in ART programmes, of whom 90% have viral load suppression) will require substantial scale-up of HIV testing services with new approaches that more effectively reach marginalised populations who are not well served by current approaches. Notable gaps in HIV Testing and Counselling (HTC) coverage exist for men, adolescents (age 16 to 19 years), rural Malawians and the poorest members of society (National Statistical Office and ICF Macro 2011).

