5.2.2 Baseline household surveys

All households in the evaluation villages will be visited for enumeration and invited to participate in the baseline household survey (PS401A). Village boundaries will be defined by obtained GPS coordinates.

An appointment will be made to visit the head of household or authorised individual to explain the study. All adults and older adolescents will be asked for verbal consent to participate, with verbal consent from guardians required in the case of adolescents.

As part of the baseline household survey, a household-level questionnaire of household size, age and gender composition, and socioeconomic indicators will be administered. Each adult household member will then be asked for verbal consent to participate in a brief individual questionnaire on demographic characteristics and experience with HIV testing and care.

A random selection of participants will then also be asked for written consent to complete an extended individual questionnaire on sexual behaviour, stigma, and health service utilisation, including costs. A discrete choice module will investigate user preferences for HIV delivery and linkage to care.

One in 4 household survey participants will be randomly allocated to a longer questionnaire (PS401B/PS402A), includes an approach to establishing user preferences by asking participants to make a series of trade-off choices (discrete choice experiment: DCE). Written or witnessed informed consent (or assent with guardian consent in the case of adolescents) will be obtained beforehand. Selection will be determined based on a random number generated by the electronic survey device at the time of the household survey (Choko, et al. 2015).

A post-intervention survey will be conducted with the same evaluation villages 12 months after the start of HIVST services. The post-intervention survey will consist of the household and brief individual questionnaires as well as an additional section on self-testing.

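### The discrete choice experiment sample of 1,000 does not give about 200 people in the named self-identified HIV-positive stratum: at the protocol's own prevalence it gives about 50 to 130

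*Protocol*

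**What the plan says.** Protocol section 7.2, under the extended individual questionnaire, presents the sample as the minimum that the DCE needs. It says that "conventional sample sizes tend to be around 200 participants per population strata", adding "though new efficient experimental designs do allow for smaller samples", and concludes: "The study will use five strata in total, generating a sample size of 1,000 participants". The strata of interest that follow are low and high HIV risk, younger and older age, "male and female, self-identified HIV positive and negative, and Socio-Economic Status (SES) quintiles".

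Section 5.2.2 fixes how people are chosen: "One in 4 household survey participants will be randomly allocated to a longer questionnaire". The mechanism is also stated: "Selection will be determined based on a random number generated by the electronic survey device at the time of the household survey". No quota, stratified draw or unequal selection probability is described. Section 5.5.3 repeats a figure of about 1,000 for the extended questionnaire, and section 1.4 puts the household survey at about 5,000 adults.

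The Background (section 2) describes Malawi "with an estimated 10.2% of adults living with HIV" and says that 46% of those people are on ART.

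**The concern.** The size is built as a number of strata times 200, but the things counted as strata are five factors, and every respondent falls in one level of each. Multiplying 200 by the number of factors does not ensure that any particular level reaches 200. Under a simple random draw, each level's size follows its share of the population, so a rare level falls short whatever the product says. Self-identified HIV-positive adults are the one named level that the protocol's own figures show to be rare.

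What is at stake is specific objective 4 (section 3.1.1), preferences for self-testing delivery and for linkage to care. People who know that they are HIV positive are the group with direct experience of linkage. A reader of section 7.2 would expect about 200 of them.

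**Working it through.** **Inputs (Protocol).** About 200 per stratum, five strata, N = 1,000 (section 7.2). One-in-four selection (5.2.2) from about 5,000 adults (1.4). HIV prevalence 10.2%, with 46% of HIV-positive people on ART (section 2).

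**Assumption.** The documents do not give the share of HIV-positive people who identify themselves as such. I take 100% as the ceiling. As a low-end value I take 46%, meaning that only those on ART do so.

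**1. The plan's own figure.** 5 x 200 = 1,000. It reproduces.

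**2. What 1,000 delivers, one factor at a time.**
- Socio-economic quintile: 1,000 x 0.20 = 200 per level.
- Two-level factor, evenly split: 1,000 x 0.50 = 500 per level.
- High HIV risk: its share is not given, so no count can be derived.

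**3. What the one-in-four draw delivers in total.** 5,000 / 4 = 1,250 selected. This agrees with 1,000 if about 80% take part (1,000 / 1,250) or if about 4,000 adults are surveyed. I use both values of N.

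**4. Expected self-identified HIV-positive respondents** = N x prevalence x share self-identifying.

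| N | 46% self-identify | 100% self-identify |
|---|---|---|
| 1,000 | 1,000 x 0.102 x 0.46 = 47 | 1,000 x 0.102 = 102 |
| 1,250 | 1,250 x 0.102 x 0.46 = 59 | 1,250 x 0.102 = 128 |

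Every entry is below 200. The range runs from about a quarter (47/200 = 0.24) to just under two-thirds (128/200 = 0.64) of the convention.

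**5. Could chance close the gap?** At N = 1,000 with everyone self-identifying, the binomial probability of 200 or more is about 3 x 10^-20. It cannot.

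**6. What would be needed.**
- Self-identified prevalence: 200 / 1,000 = 20%, or 200 / 1,250 = 16%.
- Respondents under simple random selection: 200 / 0.102 = about 1,961 if all self-identify; 200 / (0.102 x 0.46) = about 4,263 if 46% do.

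**7. Sensitivity to local prevalence.** Section 4.4 prefers high-burden sites, so 10.2% may be low for these villages. At an assumed 15%, N = 1,000 gives 1,000 x 0.15 x 0.46 = 69 to 1,000 x 0.15 = 150. N = 1,250 gives 1,250 x 0.15 x 0.46 = 86 to 1,250 x 0.15 = 188. Both stay below 200.

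**The case against.** Four points can be made in the plan's favour.

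*The total is defensible.* For one-factor-at-a-time estimates the same 1,000 people serve every factor, so the factor with the most levels sets the requirement. That is socio-economic quintile, and 5 x 200 = 1,000. This stands. A reader might infer that because the factors have 2 + 2 + 2 + 2 + 5 = 13 levels, 13 x 200 = 2,600 people are needed, or that the 80 crossed cells each need 200. The documents support neither reading: levels of different factors share respondents, and nothing in section 7.2 asks for estimates in crossed cells.

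*The 200 is a hedged convention.* Section 7.2 says that DCE sample sizes are not formalised as trial sample sizes are, and that efficient designs allow fewer. Precision also depends on how many choices each respondent makes, which section 5.2.2 does not give. This stands too. A reader might infer that 50 to 130 people are too few for the DCE, but the protocol does not allow that to be shown. The hedge names no smaller number, however, and the protocol still derives 1,000 from 200 per stratum.

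*The inputs are proxies.* The 46% is ART coverage, and people diagnosed but not on ART can also identify themselves, so 47 to 59 is a low-end figure. The 10.2% is national. Both are fair cautions, but the shortfall remains at 100% self-identification and at an assumed 15% prevalence.

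*The trial does not depend on it.* Agreed: no primary or secondary outcome, and no stated power claim, uses this stratum.

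**Conclusion.** The point holds in a limited form. The total of 1,000 can be justified by the five socio-economic quintiles, but section 7.2 presents it as about 200 in each named stratum, and the selection rule in section 5.2.2 does not deliver that for self-identified HIV-positive adults. The expected number is at most about 102 at N = 1,000 or 128 at N = 1,250. It is 47 to 59 if only those on ART identify themselves. These figures rest on 10.2% prevalence, simple random selection and an assumed self-identification share of 46% to 100%. The high-risk stratum cannot be checked, because its share is not given; it too would need to be 16% to 20% of respondents to reach 200.

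This is a mismatch between the stated basis of the sample and the sampling rule, confined to the DCE. It is not an arithmetic slip, and it does not show that the DCE is underpowered.

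**What to change.** Reword the justification in section 7.2:

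- Call the five items stratification factors, and tie 1,000 to five socio-economic quintiles at about 200 each.
- State the number expected in the HIV-positive stratum, about 50 to 130, with the assumptions behind it.
- Either give the DCE precision that this number supports for the planned number of choices per respondent, or describe that stratum's preference estimates as exploratory.
- Give the assumed share at high HIV risk, or say that it is unknown.

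This is a text change, plus one precision calculation if the first alternative is taken. It needs no extra interviews.

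Oversampling HIV-positive adults is an option, not a requirement. Of 5,000 surveyed, 5,000 x 0.102 x 0.46 = 235 to 5,000 x 0.102 = 510 would be available, so 200 means selecting 85% (200/235) to 39% (200/510) of them before refusals. At the low end, a total of 1,000 leaves 800 places for the other 4,765 adults, or about 17%. HIV-positive people would then be 20% of those selected (200/1,000) but about 1% of those not selected (35/4,000), so in a household survey selection itself would say something about status. It would also require that status be recorded before the draw, and the weighting would cost precision in the user-cost analysis, which uses the same sample (section 5.5.3).

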9.1 Confidentiality

Participants will not have their names used during any stage of data collection except in recruitment logbooks and will be given a unique identifier. Hard copies of questionnaires and transcripts will be kept in locked cupboards in a secure location in MLW and electronic transcripts will be password protected on a computer accessible only to authorised staff members.

9.2. Informed consent

Informed consent will be taken for participation in certain parts of the study. If the substudy requires that participants give written consent, the investigator will first provide the potential subject with an explanation of the study as well as an information sheet with study details. The investigator will answer any questions raised by the potential participant and allow them sufficient time to come to a decision. Participants will then be required to give consent. In cases where written consent is required and the participant is illiterate, they will be asked to give verbal consent plus a thumb print. Parental consent will be required if participants are 16 or 17 years old.

Method	Consent Requirements
Cognitive interviews	Written
Key Informant inerviews	Written
FGD	Written
IDI	Written
HIVST + HTC for pilot accuracy studies	Written
Baseline household survey	Verbal
Extended individual questionnaire	Written
Post intervention household survey	Written
PSI-led HIVST distribution	Request waiver of informed consent; leaflets provided in lieu of participant information sheets
Process evaluation	N/A
DCE	Written
Costing study	N/A

Figure 12. Consent requirements for each research activity
9.3. HTC and HIVST

All individuals selecting to self-test will be offered pre- and post-test information and referral to the most convenient clinic offering ART services. Participants will also be given the opportunity to discuss any fears about the process or results prior to testing and to disclose their status and receive advice and support for post-test services.

Participants are not required to disclose the results of HIVST to the distribution agent, but such will be encouraged so that they can receive results-based, post-test information. The only exception is during the pilot accuracy study, where self-testing will need to be disclosed in order to verify the accuracy of HIVST results against confirmatory results.

All disclosed HIV status results will remain confidential.

9.4. Compensation for participation

Study participants will be compensated for their time away from income-earning activities, but this will be packaged as compensation rather than payment. This will include refreshments, refund of any transport costs incurred. For those exposed to the HIVST intervention, the decision to self-test or not will not influence the amount of compensation.

Compensation will be as follows:

- MWK 1000 per household for participation in the Household Surveys
- MWK 1000 for individuals participating in FGDs, IDIs, cognitive interviews and pilot accuracy studies

10. Constraints and limitations

10.1. Risk mitigation

Social harms monitoring will be conducted by MLW-LSHTM and PSI throughout the HIVST distribution period to respond to incidences of coercion, GBV, and other potential unintended consequences from self-testing. Systems for tracking social harms include a community-based reporting network using community stakeholders and leaders and hotline for HIVST participants to call and report adverse events. Tracking of social harms will then enable MLW-LSHTM to assess and mitigate adverse events arising from HIVST.

10.2. Data quality

MLW-LSHTM has considerable expertise in supporting all aspects of quality data management in Malawi. Standard Operating Procedures (SOP) will be used on study design, data collection instruments and data analysis procedures, with routine data quality audits conducted for quality assurance purposes. PSI and MLW-LSHTM have also invested in electronic data collection, using open source software and computer tablets. This approach improves data collection efficiency and reduces traditional weaknesses associated with data collection such as completeness, consistency, and timeliness. Additionally, MLW has substantial experience with bridging any gaps in MoH records and project data requirements, using extraction of registers onto Optic Character Recognition forms.

The Research Governance unit in MLW will conduct periodic (usually annual) internal audits to ensure that all documentation and data capture is within acceptable international standards. Should PSI Malawi data be found to be not compliant with SOPs or fail a data quality audit, they will be required to revise their practices with close supervision from external technical staff, i.e., Regional Researchers and Health Area Research Advisors.

10.3. Governance

HIV STAR will form a Technical Advisory Group (TAG) to review data and provide expert opinion on whether a product should be pre-qualified, and to support post-market surveillance reports and supervision when products enter the market place.

HIV STAR has the support of key officials in the Government of Malawi. The MoH has collaborated in a number of HIVST projects to date and supported publications and presentations from projects hosted by MLW. The Director of the Department of HIV and AIDS of the MoH, is a collaborator with the MLW HIVST project and has provided a letter of support for the UNITAID project.

11. Capacity building and training

This research will contribute to qualitative and quantitative data capacity at the College of Medicine both in terms of establishing a resource base of qualified and trained researchers to conduct qualitative and quantitative fieldwork and a system for accurate and timely transcription and translation services and data management.

Data and field staff employed on the project will be trained in both qualitative and quantitative techniques, in Good Clinical Practice, and on the protocol, and will be uniquely placed to understand the complementarity of triangulation between quantitative and qualitative methods.

12. HIV STAR Malawi Budget

13. Budget justification

14. HIV STAR-M Work Plan

																	١	(2					
Activities	Lead	Group	Dec	Jan	Feb	Mar	Apr	May	Jun	Jul	Aug	Sep	Oct	Nov	Dec	Jan	Feb	Mar	Apr	May	Jun	Jul	Aug
A. CRT																							
Partner with MoH to select evaluation clinics and																							
villages	PI/LC/PM	MLW/PSI																					
Meet with community leaders and clinics to explain study	PM	PSI/MLW																					
Develop database for quantitative data	DM/PI	MLW																					
Identify and obtain GPS coordinates for village and househould boundaries	PM/PI	PSI/MLW																					
Train field/data team on tools and SOPs	PI/DM/PM	MLW/PSI	Ì									Ì											
Train ART clinic staff on tools and SOPs												Ì											
Train CBDAs on tools and SOPs	PI/PM	MLW/PSI																					
Randomly assign intervention to evaluation villages	PI/LC	MLW																					
Collect and analyse data for baseline household survey																							
Pilot baseline survey and revise based on feedback	PI/PM	MLW/PSI																					
Enumerate households and randomly recruit participants for extended survey	PM/PI	PSI/MLW																					
Pilot extended baseline questionnaire and revise based on feedback	PI/PM	PSI/MLW																					
Conduct extended baseline questionnaire	PM/PI	PSI/MLW										1											
Conduct quality and accuracy checks on incoming electronic data	PI/DM	MLW																					
Clean quantitative data	DM/PI	MLW										Ì											
Conduct preliminary analysis of quantitative data	PI/LC/MN	MLW/LSHTM										Ì											
Generate preliminary report on baseline findings	PI/LC	MLW																					
Conduct in-depth analysis of quantitative data	PI/LC/MN	MLW/LSHTM																					
Generate in-depth report on baseline findings	PI/LC	MLW																					
Collect and analyse data for interim household survey																							
Pilot extended interim household survey and revise based on feedback	PI/PM	PSI/MLW																					
Conduct interim household survey	PM/PI	PSI/MLW																					
Conduct quality and accuracy checks on incoming electronic data	PI/DM	MLW																					
Clean quantitative data	DM/PI	MLW																					
Conduct preliminary analysis of quantitative data	PI/LC/MN	MLW/LSHTM																					
Generate preliminary report on interim findings	PI/LC	MLW																					

	1	1	1	 	-	1	1	() (1	ſ	 	1			i	1	
Conduct in-depth analysis of quantitative data	PI/LC/MN	MLW/LSHTM		 								 						
Generate in-depth report on interim findings	PI/LC	MLW																
Collect and analyse data from CBDAs and ART clinics																		
Pilot CBDA tools in intervention villages and revise																		
based on feedback	PI/PM	MLW/PSI		 														
Collect SCQs and HIVST registers and kits from CBDAs in intervention villages	PI/PM/CC	MLW/PSI																
Collect harms monitoring records from community	PI/PIVI/CC	IVILVV/P3I										 						
leaders in intervention villages	PI/PM/CC	MLW/PSI																
Collect patient registers and referral forms from ART	, ,																	
clinics	PI/PM/CC	MLW/PSI																
Enter paper-based data into electronic files	DM	MLW																
Conduct quality and accuracy checks on incoming																		
electronic data	PI/DM	MLW		 	_													
Clean quantitative data	DM/PI	MLW																
Conduct preliminary analysis of quantitative data	PI/LC/MN	MLW/LSHTM																
Generate preliminary report on impact evaluation									Ì									
findings	PI/LC	MLW		 														
Conduct in-depth analysis of quantitative data	PI/LC/MN	MLW/LSHTM																
Generate in-depth report on impact evaluation																		
findings	PI/LC	MLW																
B. COGNITIVE INTERVIEWS				 			1			- î		 	1	ŕ				
Partner with MoH to select health facilities	PI/LC	MLW										 						
Meet with clinic staff and community leaders to ensure project buy-in	PI/LC	MLW																
Train SS-RA on tools and SOPs	PI/ND	MLW-SS																
Pilot tools and revise based on feedback	PI/SS-RA	MLW-SS																
Identify and recruit study participants	SS-RA/PI	MLW-SS																
Conduct cognitive interviews	SS-RA/PI	MLW-SS							ĺ									
Conduct quality checks on collected data	PI/TT	MLW-SS																
Enter paper-based data into electronic files	DM/TT	MLW-SS													 			
Conduct ongoing analysis of qualitative data and		IVILVV-35																
iteratively revise IFUs	PI/ND/LC	MLW-SS																
Generate report on findings with recommendations									j									
on prototype IFUs/IEC materials	PI/ND/LC	MLW-SS																
C. KEY INFORMANT INTERVIEWS																		
Conduct document review on HIV policy and																		
regulation	SRA	LSTM										 						
Identify and recruit HIV policy and regulation stakeholders	SRA/ND	LSTM/MLW- SS																
Conduct KII with HIV policy and regulation	SNAJND																	
stakeholders	SRA	LSTM																
Transcribe interviews into electronic files	Π	LSTM							j									
Clean and code qualitative data	SRA	LSTM																
	SRA/ND	LSTM/MLW																
Conduct analysis of qualitative data																		

Generate report on findings with recommendations		LSTM/MLW-	 						 			-			
on policy/regulatory actions	SRA/ND	SS													
D. PILOT STUDY			ł	ł	I	I	I			 			·	 -	
Partner with MoH to select pilot villages	PI/LC	MLW						Ì							
Meet with community leaders to ensure project buy-	,													 	
in	PI/LC	MLW													
Train field and data team on tools and SOPs	PI	MLW													
Develop database for quantitative data	DM/PI	MLW													
Identify and obtain GPS coordinates for village and househould boundaries	FM/PI	MLW													
Collect and analyse data for mapping exercises															
Conduct transect walks and mapping exercises in pilot villages	SS-RA/PI	MLW-SS													
Enter paper-based data into electronic files	тт	MLW-SS													
Conduct analysis of qualitative data	PI/ND/LC	MLW-SS													
Develop pilot social harms reporting system	PI/ND/LC	MLW-SS													
Collect and analyse data for feasibility, acceptability and accuracy study															
Identify and recruit households for accuracy study	FM/PI	MLW													
Identify and recruit peer organisations for accuracy study and FGDs	FM/PI/SS- RA	MLW-SS													
Identify and recruit household members for IDIs	FM/PI/SS- RA	MLW-SS													
Pilot tools and revise based on feedback	PI/FM/SS- RA	MLW-SS													
Conduct HTC/HIVST for accuracy study	FM/PI	MLW													
Conduct FGDs with peer groups	SS-RA/PI	MLW-SS													
Conduct IDIs with adults from randomly selected households	SS-RA/PI	MLW-SS													
Conduct quality and accuracy checks on collected data	PI/DM	MLW													
Enter paper-based data into electronic files	DM	MLW													
Clean quantitative data	DM/PI	MLW													
Transcribe and translate qualitative data	Π	MLW-SS						ĺ							
Clean and code qualitative data	SSA	MLW-SS						İ							
Conduct preliminary analysis of quantitative data	PI/LC/MN	MLW/LSHTM						İ							
Conduct ongoing analysis of qualitative data	PI/ND/LC	MLW-SS						Ì							
Generate preliminary report on pilot findings	PI/LC/ND	MLW						ĺ							
Conduct in-depth analysis of quantitative data	PI/LC/MN	MLW/LSHTM						ĺ							
Conduct in-depth analysis of qualitative data	SSA/ND	MLW-SS						ĺ							
Generate in-depth report on pilot indings	PI/LC/ND	MLW						Ī							
E. PROCESS EVALUATION															
Agree on key indicators and M&E data to be collected by PSI	PI/DM/MEO	MLW/PSI													

Assist DCI in double ping MARE data collections to all and	1		1	,	1				 		 	 		
Assist PSI in developing M&E data collection tools and database	PI/DM/MEO	MLW/PSI												
Extract M&E data from PSI	DM/MEO	MLW/PSI												
Conduct preliminary analysis of M&E data	PI/LC	MLW												
Generate preliminary report on findings	PI/LC	MLW												
Conduct in-depth analysis of M&E data	PI/LC	MLW												
Generate in-depth report on findings	PI/LC	MLW												
F. DCE														
Collect and analyse data for DCE formative research (embedded in pilot study)														
Conduct DCE FGDs	RA-SS/PI	MLW-SS												
Develop scenarios and illustrations based on FGDs	FTP/PI	LSHTM/MLW												
Conduct DCE IDIs	RA-SS/PI	MLW-SS												
Conduct preliminary analysis of qualitative data	SRA/ERA	LSHTM/MLW												
Generate preliminary report on DCE findings	SRA/ERA	LSHTM/MLW												
